
### Power calculations

We expect up to 18 subjects will be enrolled in this phase I with cohort expansion study. For Aim 1, up to 18 subjects will have 80% and 98% power to detect an effect size of 0.7 and 1.0 at a two-sided significance level of 5%. The one-sample t-test is used. For Aim 2 and 3, the maximum power is obtained when the sample size of two groups is identical (i.e., 9 subjects per group). For each endpoint of Aim 2 and 3, the study will have 85% power to detect an effect size of 1.5 at a two-sided significance level of 5% when sample size of each group is 9. If the sample

size of one group deviates from 9, the statistical power will decrease, accordingly. Two sample t-test is used for Aim 2 and 3, and no multiplicity adjustment is considered for power analyses.

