# 4.4 END OF STUDY DEFINITION

The phase I portion of the study will continue until reaching the MTD to determine the RP2D. The phase II portion of the study will continue until an additional 10 patients are treated at the RP2D. The maximum total number of patients enrolled in this study will be 28 (6 per dose level plus 10 in the expansion cohort). We expect that the accrual rate will be one patient per every 5-6 weeks. With the DLI observation window (56 days after DLI), the dose-escalation portion may take up to a maximum of 2.5 - 3 years to complete and an additional 1.5 years for the expansion cohort.

A participant is considered to have completed the study if he or she has completed all phases of the study including the last visit or the last scheduled procedure shown in the SOA, Section 1.3.

The end of the study is defined as completion of the last visit or procedure shown in the SOA in the trial globally.

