### **Dose-Expansion Cohorts**

Once the RP2D is reached, a total of10 patients will be treated at this dose. For the expansion cohort, patients will continue to be monitored for occurrence of DLT. If 2 of the first 5 patients or if  $\geq$  2 of 6 patients experience DLT, the PI will discuss with all study investigators and with CTEP whether further addition of patients is needed to reassess the RP2D.

Monitoring of safety and toxicity data will be captured in OnCore, Moffitt's clinical trials database.

Dose-limiting toxicities are defined as any of the following that is at least possibly attributable to the investigational treatment:

- 1. Grade 2-4 infusion toxicity
- 2. Grade 4 organ toxicity (as defined by NCI CTCAE v 5.0), not preexisting, not due to the primary malignancy, and not due to chemotherapy or infection
- 3. Grade 3 organ toxicity that does not resolve within 14 days and that is not preexisting, not due to the primary malignancy, and not due to chemotherapy or infection
- 4. Grade 2-4 acute GvHD
- Delayed neutrophil recovery: ANC >500/μl does not occur within 56 days AND measurable donor chimerism is >5%
- 6. Grade 3-4 cytokine release syndrome (CRS) (see Appendix C) (75)
  Any grade 5 reaction other than progressive disease

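### The correlative power paragraph uses the escalation maximum of 18 as the whole study, and its 85% for Aim 3 rests on a 9 v 9 severe-CRS split that the DLT rules make very unlikely

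*Combined protocol and SAP*

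**What the plan says.** All references are to the combined protocol and SAP.

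- **Study size for the correlatives.** The power paragraph closing section 8.3.1 opens with "We expect up to 18 subjects will be enrolled in this phase I with cohort expansion study".
- **Aims 2 and 3.** It says that "the maximum power is obtained when the sample size of two groups is identical (i.e., 9 subjects per group"), and that for each endpoint "the study will have 85% power to detect an effect size of 1.5", which holds for a 5% two-sided test and nine patients on each side. It adds that if the "size of one group deviates from 9, the statistical power will decrease, accordingly", without giving a figure for any other split. It closes: "Two sample t-test is used for Aim 2 and 3, and no multiplicity adjustment is considered for power analyses".
- **Aim 1.** It gives 80% and 98% power at effect sizes 0.7 and 1.0 for a one-sample t-test with up to 18 subjects.
- **Groups compared.** Aim 2 compares patients who reach remission with those who do not. Aim 3 compares patients with and without severe CRS and names the Satterthwaite t-test. Aim 3 does not define severe.
- **DLTs.** The list in section 6.1.4 includes "Grade 3-4 cytokine release syndrome (CRS"), and Appendix F repeats the item.
- **Trial size elsewhere.** Sections 4.3, 6.1.3 and 9.4.2 give 18 as the maximum for dose escalation. The synopsis expects 15 patients in phase Ib and 10 in phase II. Section 4.4 says: "The maximum total number of patients enrolled in this study will be 28". The Aim 1 text has every enrolled patient sampled, so it does not restrict the correlatives to escalation patients.

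**The concern.** Two inputs to the paragraph do not fit the rest of the protocol.

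The first is N. The paragraph says it covers the study with its expansion cohort but uses the ceiling for escalation alone.

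The second is the split for Aim 3. Severe CRS is an outcome that the design works to keep rare: at grade 3 or higher it is a DLT, and escalation stops after very few of them. A power figure that needs half the patients to have severe CRS is a poor guide to what Aim 3 can show.

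The risk is in interpretation. Aim 3 is meant to settle whether IL-6 is the main driver of toxicity or whether other cytokines are better targets. A null result read against 85% power would carry more weight than the data could support. For Aim 1 the error runs the other way, because power is understated if more than 18 paired samples are obtained.

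**Working it through.** **Inputs.** Two-sided 5% level; effect sizes 0.7 and 1.0 (Aim 1) and 1.5 (Aims 2 and 3), in standard deviation units; N = 18 (section 8.3.1), 25 expected (15 + 10, synopsis), 28 maximum (section 4.4). Both groups are assumed to have the same standard deviation.

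**Formulas.** Power = P(|T| > t₀.₉₇₅), with T noncentral t.
- One sample: noncentrality λ = d√n, df = n − 1.
- Two samples, pooled: λ = d√(n₁n₂/(n₁+n₂)), df = n₁ + n₂ − 2.
- Satterthwaite power was obtained by simulation.

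**1. The plan's own figures.** At 9 v 9, λ = 1.5 × √(81/18) = 3.18, df = 16, critical value 2.12: power 84.8%, against 85% stated. Aim 1 at n = 18 gives 79.9% and 97.9%, against 80% and 98%. All reproduce.

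**2. Aim 1 at d = 0.7, by evaluable pairs.** 18 pairs 80%; 20 pairs 84%; 22 pairs 88%; 25 pairs 92%.

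**3. Most severe-CRS cases in escalation.** Take severe as grade 3 or higher, and suppose every DLT is CRS. Under sections 4.3, 6.1.3 and 9.4.2:
- Levels 1 and 2 are passed only at 0/3 or 1/6, so each contributes at most 1.
- Level 3 can contribute at most 1/3 followed by 3/3, which is 4/6.
- Total: 1 + 1 + 4 = 6 of 18.

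**4. Likely number.** Every 3+3 path was enumerated under those sections for assumed true DLT rates from 5/10/20% to 50/50/50% across the three levels. Expected DLTs of all kinds were 1.3 to 2.5, among about 5 to 11 patients. In simulations that add the expansion cohort with its section 9.4.4 monitoring, the average was roughly 3 to 4, again from all causes.

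**5. Aim 3 power at d = 1.5.**

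| Severe cases | N = 18 pooled | N = 18 Satterthwaite | N = 25 pooled | N = 25 Satterthwaite |
|---|---|---|---|---|
| 2 | 47% | 32% | 50% | 31% |
| 3 | 61% | 42% | 65% | 41% |
| 4 | 70% | 57% | 75% | 57% |
| 5 | 76% | 69% | 82% | 71% |
| 6 | 80% | 76% | 87% | 80% |

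Example: 3 v 22 gives λ = 1.5 × √(66/25) = 2.44, df = 23, pooled power 65%. The choice of test matters when one group is small. At 3 v 22 an effect size of 1.81 gives 80% with the pooled test but about 51% with the Satterthwaite test.

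**6. Aim 2.** The protocol cites complete response rates of 36% to 52%. Of 18 that is about 6 to 9 responders, for 80% to 85% pooled power. Of 25 it is 9 to 13. At 9 v 16, λ = 1.5 × √(144/25) = 3.60, for 93%; at 13 v 12, λ = 1.5 × √(156/25) = 3.75, for 95%.

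**The case against.** The paragraph can be defended on several grounds.

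- **The arithmetic is right and the figure is conditional.** It is presented as the maximum, for 9 per group, with a warning that power falls otherwise. This stands: there is no calculation error. But the warning gives no size for the loss, and does not say that for Aim 3 the safety rules themselves force the imbalance.
- **Nine severe cases are not impossible.** A reader might infer from the limit of 6 that 9 v 9 cannot happen. The documents do not support that. The section 6.1.4 table adds three patients at the next lower level, which opens a path to 3/6 + 3/6 + 4/6 = 10 of 18. DLTs also continue to be counted in the expansion cohort: 6 in escalation plus the 4 at which section 9.4.4 Table 1 holds enrolment makes 10. Both routes are remote. The chance of 9 or more is at most about 0.02% through the backfill, over the non-decreasing DLT rates searched, and 0.5% or less for the whole trial in the scenarios simulated.
- **Nine are not needed at the right N.** A reader might also infer that 85% always requires 9 severe cases. That holds only at N = 18. At N = 25, 6 cases give 87% pooled and 80% Satterthwaite, and 7 give 90% and 86%. Even 6 v 12 loses only about 4 points with the pooled test. The large loss comes at 2 or 3 cases, which is where the rules point.
- **Severe CRS is undefined in Aim 3.** If it included grade 2, the DLT limit would not apply. Grade 3 or higher is the natural reading, because it is both the DLT threshold and the SAE threshold in section 8.4.3.3.3, but it remains an assumption.
- **Little depends on it.** The correlatives run as funding permits, are described as exploratory, and drive no dose, stopping or efficacy decision. This stands and limits the importance of the point.

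**Conclusion.** The point holds in a limited form.

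**N.** This needs no assumption. Eighteen is the escalation maximum, and the study with its expansion cohort is 25 expected and 28 at most.

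**Aim 3.** If severe CRS means grade 3 or higher, a 9 v 9 split is out of reach in escalation under sections 4.3, 6.1.3 and 9.4.2, and very unlikely by any other route. A handful of severe cases is the realistic expectation. With 2 or 3, power at an effect size of 1.5 is about 31% to 41% with the planned test at N = 25 (50% to 65% pooled), not 85%. Correcting N does not rescue this: with 3 cases, Satterthwaite power is 42% at N = 18 and 41% at N = 25.

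**What does not follow.** The 85% is not miscalculated, and the objection does not extend to Aim 2, where a near-even split is plausible. Nor can a single 92% be claimed for Aim 1: it requires all 25 patients to supply both samples, while the schedule of activities lets tests be omitted at the physician's discretion.

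The figures rest on equal standard deviations in the two groups and on assumed DLT rates. The backfill in section 6.1.4 does not appear in sections 4.3, 6.1.3 and 9.4.2. Appendix F allows accrual to a higher level while patients at the lower level are not yet evaluable, whereas section 9.4.2 requires all patients at a level to be observed first. These sections must be reconciled before any exact limit on DLTs is quoted.

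**What to change.** Rewrite the power paragraph in section 8.3.1:

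1. State N as 25 expected (28 maximum), or state that only escalation patients are sampled.
2. Give Aim 1 power by number of evaluable pairs, as in step 2 of the working.
3. State the definition of severe CRS used in Aim 3.
4. Replace the 85% for Aim 3 with power by number of severe cases, from 2 to 6, using the planned Satterthwaite test. The N = 25 columns of the table can be used, with the pooled figures labelled as such.
5. Keep the near-balanced calculation for Aim 2 only, recomputed at the corrected N.

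The cost is one paragraph and a less favourable Aim 3 figure. Aims 1 and 2 become more favourable. No extra patients, samples or changes to trial conduct are needed.

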#### 8.4 ADVERSE EVENTS AND SERIOUS ADVERSE EVENTS

#### 8.4.1 DEFINITION OF AE

AE means any untoward medical occurrence associated with the use of an intervention in humans, whether or not considered intervention related—21 CFR 312.32 (a). An adverse event may include any unfavorable and unintended sign (including an abnormal laboratory finding), symptom or disease temporally associated with the use of a medical treatment or procedure regardless of whether it is considered related to the medical treatment or procedure (attribution of unrelated, unlikely, possible, probable, or definite).

#### 8.4.2 DEFINITION OF SAE

An SAE is any sign, symptom or medical condition that emerges during treatment or during a post-treatment follow-up period that (1) was not present at the start of treatment and is not a chronic condition that was part of the patient's medical history, OR (2) was present at the start of treatment or as part of the patient's medical history but worsened in severity and/or frequency during therapy, AND that meets any of the following regulatory criteria:

- is fatal (i.e., results in death from any cause at any time) or life-threatening (i.e., the patient was in the view of the investigator, at immediate risk of death from the reaction as it occurred)
- required or prolonged hospitalization (see exclusions below)
- results in persistent or significant disability/incapacity
- constitutes a congenital anomaly or a birth defect
- is medically significant, may jeopardize the subject and may require medical or surgical intervention to prevent one of the outcomes listed above.

Events not considered to be SAEs are hospitalizations for the:

- Routine treatment or monitoring of the studied indication, not associated with any deterioration in condition
- Treatment, which was elective or pre-planned, for a preexisting condition that did not worsen

Serious adverse events occurring in a patient from the first day of treatment and until 4 weeks after the last dose of treatment must be reported. The period after discontinuing study drug may be extended if there is a strong suspicion that the drug has not yet been eliminated.

All serious adverse events must be followed to resolution (≤ 1 or baseline) or until considered stable or irreversible.

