# 1.3 SCHEDULE OF ACTIVITIES (SOA)

For explanation of procedures, please see Section 8 (Study Assessments and Procedures).

· · · · · · · · · · · · · · · · · · ·	Initial	Allowable time from start of induction	Starting Day 0	Day 28	Day 42	Day 56	6 months +/- 2 weeks	1 yr +/- 2 weeks
History and physical	Х	Within 30 days			Х	Х	X	X
Performance status	Χ	Within 30 days						
Staging Bone Marrow Biopsy and aspirate for research	Х	Within 30 days			X a			
Peripheral blood for research	Х		Daily days 0-7		X a			
CBC & Diff	x	Within 7 days	ANC<50 0- 3x/week ANC≥50 0- weekly to day 56		×	×	×	x
СМР	Х	Within 7 days	Weekly to day 56		Х	Х	Х	Х
CXR or Chest CT	Х	Within 30 days						
Pregnancy test (women, childbearing age)	Х	Within 30 days						
Human Immunodeficiency Virus	Х	Within 30 days						
EKG	Х							
MUGA or ECHO	Х	Within 30 days						
HLA typing	Χ							
Anti-donor HLA antibody testing	Χ				Χ			
Adverse Event Monitoring			Weekly to day 56		х	х	×	X
GvHD evaluation			At onset, weekly until resolves		х	х		
Peripheral blood or bone marrow for donor chimerism					Xa	Xp		
CMV IgG	Х	Within 30 days						
CMV PCR			Weekly through day 56					
C Reactive Protein	Х	Within 7 days	Weekly through day 56		_			
Ferritin	Х	Within 7 days	Weekly through day 56		х	х		

Abbreviations: ANC, absolute neutrophil count; CBC, complete blood count; CMP, comprehensive metabolic panel; CMV, cytomegalovirus; CXR, chest radiograph; CT, computerized tomography scan; diff, differential blood count; ECHO, echocardiogram; EKG, electrocardiogram; GvHD, graftversus-host disease; MUGA, multigated acquisition; PCR., polymerase chain reaction

Tracking of days begins from day of cell transfusion (eg, Day 56 is 56 days after initial cell infusion). Day of cell transfusion is marked as Day 0. Procedures can be performed  $\pm$  3 days from marked date, unless otherwise specified. aSpecified day 42 samples may be performed prior to day 42 if the patient has recovered from aplasia, defined as ANC >500/µl. Otherwise, the specimen collections will be planned for day 42 +/-3 days. b Day 56 chimerism measurement may be omitted if donor T-cell chimerism is < 5% on first measurement or if whole blood/marrow chimerism is < 5% when T-cell chimerism is not measurable. If donor chimerism >5% on day 56, then the investigator will continue performing monthly GVHD evaluations and chimerism until donor T-cell chimerism decreases to <5% or until 1 year, whichever comes first.

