### 6.1.3 DURATION OF THERAPY

Subjects are eligible for only one lymphocyte infusion. For the dose-escalation portion, a minimum of 2 subjects and a maximum of 18 subjects will be enrolled. There will be 3 dose levels in the dose-escalation portion. MTD is defined as the highest dose level with the probability of DLT less than 33% (DLT events are defined in Section 6). The DLT observation window is defined in section 9.4.2. If none of 3 patients experiences a DLT, we will escalate to the next dose level. If one of the 3 patients experiences a DLT, we will enroll 3 additional patients and treat at the same dose level. In this case, if none of these additional 3 patients experiences a DLT, we will escalate to the dosage to next level. If 2 or more patients among 6 enrolled patients experience a DLT, or 2 or more patients in the

3 patient cohort experience DLT, the dosage level exceeds the MTD and the previous dose level will be declared as the MTD. If the first dose level exceeds the MTD, the study will be suspended. If no subjects experience a DLT at any dose level, the MTD will be level 3 (5 x  $10^7$  CD4+ T cells/kg).

The RP2D is defined as the dose level selected to be evaluated in the expansion cohort or future phase II studies and will be equivalent to the MTD determined in the phase 1b portion of the study. Once we determine the RP2D level, we will enroll 10 additional eligible patients and treat with the RP2D level. The goal for this expansion cohort is to evaluate the safety and tolerability for patients who will be treated with NE-DLI in the RP2D dose level, and to evaluate the preliminary efficacy estimate for the ORR. Including the dose-escalation portion in which 3 or 6 enrolled patients will have been treated at the RP2D level, a total of at least 13 patients will be treated at the RP2D level. Based on previous data, (18) the complete response rate using microtransplantation was in the range of 36%-52% for MDS or AML from antecedent MDS patients. Hence, for the phase 2 portion, an ORR of 45% is considered clinically meaningful. With a sample size of 13 patients, if our ORR is 45%, the 95% CI (exact binomial) will be (18%-74%); if the ORR is 50%, the 95% CI will be (22%-78%).

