#### 8.4.3.3 ADVERSE EVENTS NOT ATTRIBUTABLE TO THE DEVICE

Four categories of device non-attributable adverse events will be monitored and, if necessary, reported: 1) non-hematologic toxicities; 2) GvHD; 3) DLI-induced aplasia; and 4) CRS. Reportable adverse events are defined as non-hematologic toxicities requiring hospitalization, grade 3 or 4 toxicities defined below, and grade II acute GvHD.

Adverse events that are not considered serious will be included in the annual report. Serious adverse events include any death within the first 56 days after DLI, grade 2-4 acute GvHD, DLI-induced aplasia, ≥grade 3 CRS, and any adverse event that is deemed to be significant by the PI.

Non-hematologic toxicities will be monitored daily while patient remains admitted (typically until ANC exceeds 500/microliter, which usually occurs between days 21 and 42), then at clinic visits on day 42, day 56, 6 months, and

1 year. Toxicities will be graded using the National Cancer Institute's Common Terminology Criteria for Adverse Events (CTCAE) Version 5.0.

The following is a list of categories that will not be required to be recorded unless the event becomes a grade 4:

- Allergy/Immunology
- Auditory/Hearing
- Cardiovascular (Arrhythmia)
- · Cardiovascular (General)
- Coagulation
- Constitutional symptoms
- Dermatology/Skin
- Endocrine
- Hemorrhage
- Hepatic
- Infection/Febrile neutropenia
- Lymphatics
- Metabolic/Laboratory
- Secondary Malignancy
- Sexual/Reproductive Function

A toxicity in the following categories will be captured as an adverse event if it reaches grade 3 or grade 4:

- Gastrointestinal
- Musculoskeletal
- Neurology
- Ocular/Visual
- Pain
- Pulmonary
- Renal/Genitourinary

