#### 8.4.3.3.2 DONOR LYMPHOCYTE INFUSION-INDUCED APLASIA

DLI-induced aplasia is defined as neutropenia (ANC <500/mL) on day 42 with evidence of donor chimerism (>5%) on the day 42 sample collection. In the case of DLI-induced aplasia diagnosed on day 42, a second chimerism analysis will be sent on day 56 to confirm. All cases of DLI-induced aplasia persisting to day 56 will be reported as serious adverse events.

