#### 8.4.5 AE REPORTING

The PI and/or the research nurse will monitor each patient closely for the development of adverse events and toxicities and record all such events. AEs will be recorded and reported in our annual report. As some toxicities are expected from the chemotherapy, we will compare incidence of toxicities to historical experience when using chemotherapy without the investigational DLI product. The FDA require the timely reporting of adverse events (including toxic deaths).

Each individual sign or symptom must be documented separately. Grade 3-5 adverse events (both expected and unexpected) will be captured on the appropriate study-specific CRFs.

An investigator must verify the attribution of all adverse events. Evaluation of laboratory toxicities may be documented on CRF provided the investigator signs it. However, if an action was conducted due to this abnormality (e.g., red blood cell transfusion due to low hemoglobin) this would be recorded on the AE form also.

AE reporting will begin at the time of cell infusion and continue through 1 year from day 0 or until loss to followup, death, disease progression, or proceeding to allogeneic BMT, whichever comes first. Subjects who proceed to allogeneic BMT will come off of the trial and will no longer be followed for AEs.

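### Section 8.4.2 ends mandatory SAE reporting at day 28, which contradicts the protocol's own later SAEs and its other reporting clauses

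*Combined protocol and SAP*

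**What the plan says.** Section 8.4.2 sets a reporting period specifically for SAEs: from the first day of treatment, "until 4 weeks after the last dose of treatment must be reported". It adds a discretionary extension: "The period after discontinuing study drug may be extended if there is a strong suspicion that the drug has not yet been eliminated". Section 6.1.3 fixes the number of doses: "Subjects are eligible for only one lymphocyte infusion". Section 1.3 fixes the clock: "Day of cell transfusion is marked as Day 0".

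The protocol's own SAE designations run later:

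- Section 8.4.3.3: "Serious adverse events include any death within the first 56 days after DLI". The same list names grade 2-4 acute GvHD, DLI-induced aplasia and CRS of grade 3 or higher.
- Section 8.4.3.3.1 treats every case of grade 2-4 acute GvHD as an SAE. It continues GvHD monitoring until donor T-cell chimerism is below 5% or 1 year has passed.
- Section 8.4.3.3.2: "DLI-induced aplasia is defined as neutropenia (ANC <500/mL) on day 42", with donor chimerism above 5% on that sample. It then says: "All cases of DLI-induced aplasia persisting to day 56 will be reported as serious adverse events".

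Three further sections deal with reporting. Section 8.4.4 covers AEs and SAEs and has all events reported until transplant conditioning, relapse, death or 1 year. Section 8.4.5 says: "AE reporting will begin at the time of cell infusion and continue through 1 year from day 0", with earlier stops. Section 8.4.6 requires immediate reporting of any SAE to the FDA and gives no end date.

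**The concern.** Section 8.4.2 is the only clause that gives a period for SAEs by name, and section 8.4.3.1 refers to 8.4.2 when it describes the decision on expedited reports. Staff who follow it literally could treat a serious event in week 6 as outside mandatory SAE reporting and leave it to the annual report that section 8.4.5 describes for AEs. Staff who follow 8.4.4 or 8.4.6 would report the same event at once.

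Timeliness matters because SAE reports are one of the routes to oversight. Section 10.1.5 sends SAEs concurrently to the IRB and the sponsor and has the Protocol Monitoring Committee review them. The scheduled safety reports to that committee follow odd-numbered dose levels, so none is scheduled on completion of level 2 unless the committee asks for one.

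A second mismatch concerns aplasia. Section 8.4.3.3 lists it as an SAE without qualification, while 8.4.3.3.2 reports it as one only if it persists to day 56.

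**Working it through.** No power or sample-size figure is at issue. The check is calendar arithmetic, followed by a comparison of the clauses.

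**Step 1: end of the 8.4.2 period.** There is one infusion (6.1.3) on day 0 (1.3). Taking treatment to mean that infusion, 0 + 4 × 7 = day 28.

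**Step 2: position within the DLT window.** Section 4.3 gives 56 days. Sections 9.4.2 and Appendix F make 56 days the maximum, with earlier closure on neutrophil recovery plus donor chimerism below 5%. Against that maximum, 28/56 = 0.50, so days 29 to 56 (28 days) lie outside the 8.4.2 period. Section 8.4.3.3 puts usual neutrophil recovery between days 21 and 42, so some patients' DLT windows may close before day 28.

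**Step 3: the protocol's SAEs against day 28.**

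| SAE | When it can arise | Relation to day 28 |
|---|---|---|
| Death to day 56 (8.4.3.3) | Days 0-56 | Days 0-28 inside, days 29-56 outside |
| Grade 2-4 acute GvHD (8.4.3.3.1) | No day limit | Partly outside |
| CRS grade 3 or higher (8.4.3.3.3) | No day limit; section 8.3.1 expects CRS in the first 7 days | Mostly inside |
| DLI-induced aplasia (8.4.3.3.2) | Diagnosed day 42, SAE at day 56 | Wholly outside |

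For aplasia, 42 − 28 = 14 days after closure. With the ±3-day visit allowance in section 1.3, the earliest diagnosis is day 42 − 3 = 39, and 39 − 28 = 11 days after closure. Sampling earlier than that is allowed only for patients who have already recovered their counts, who are not aplasia cases. Confirmation falls 56 − 28 = 28 days after closure. One listed SAE is therefore wholly outside the period, and deaths and GvHD are partly outside.

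**Step 4: the reporting clauses side by side.**

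| Section | Start | End |
|---|---|---|
| 8.4.2 | First day of treatment | 4 weeks after last dose; may be extended |
| 8.4.4 | Start of study intervention | First of transplant conditioning, confirmed relapse, death, 1 year |
| 8.4.5 | Cell infusion | First of 1 year, loss to follow-up, death, progression, allogeneic BMT |
| 8.4.6 | Not stated | Not stated |

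The four do not agree on start or end. Take a patient who relapses after day 28 and dies by day 56. Section 8.4.3.3 makes that death an SAE. It falls after the 8.4.2 limit, and after the relapse or progression that ends the 8.4.4 and 8.4.5 periods. Only 8.4.6, which has no limit, reaches it.

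**Step 5: does another meaning of treatment remove the conflict?** Section 8.4.2 does not define the word. If consolidation chemotherapy counted, the last dose would be later for some patients. Section 6.1.2.2 allows consolidation only after neutrophil recovery and for patients in remission. A patient who is still neutropenic on day 42 has not met that condition, so aplasia stays outside on this reading too.

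**The case against.** The strongest reply is that later SAEs are still reportable. Section 8.4.2 is headed as a definition, whereas SAE reporting is the subject of 8.4.6, which has no day limit. Section 8.4.4 names SAEs, runs up to 1 year and requires inquiry about them at each visit. Sections 8.4.3.3.1 and 8.4.3.3.2 designate later SAEs in specific terms. Section 8.4.2 itself counts a fatal event at any time as serious and allows its period to be extended. This stands to the extent that the protocol, read as a whole, does not stop SAE reporting at day 28. It does not make the clauses agree. The extension is optional and tied to drug elimination, a test that fits a cell product poorly and does not mention death, GvHD or aplasia.

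A reader might also infer that late deaths, GvHD and aplasia would go unreported while the next dose level is being decided. The documents do not support that. Escalation depends on DLT evaluation, not on the 8.4.2 period: section 9.4.2 requires every patient at a level to be observed through the DLT window first, and Appendix F requires full evaluation. Attributable grade 2-4 GvHD, failure of neutrophil recovery by day 56 with chimerism above 5%, and grade 5 reactions other than progressive disease are all DLTs. AE monitoring is weekly to day 56 (section 1.3), and the monitoring committee reviews adverse events monthly (section 6.4).

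**Conclusion.** The point holds as an internal contradiction in a stated rule. The 8.4.2 limit of day 28 conflicts with 8.4.3.3, 8.4.3.3.1, 8.4.3.3.2, 8.4.4 and 8.4.6. All DLI-induced aplasia lies outside it, as do deaths on days 29 to 56 and any GvHD after day 28. The consequence is possible late or inconsistent SAE reporting to the monitoring committee, the IRB and the FDA. It should be corrected, but it does not undermine the dose-escalation data.

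The day-28 result assumes that treatment means the single infusion and that the optional extension is not used. The 50% figure is relative to the maximum DLT window, and a patient whose window closes early has less of it uncovered, or none.

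Two further inferences go too far. One is that several listed SAEs cannot occur by day 28; that is true only of aplasia, since death and GvHD can occur on either side. The other is to project deaths on days 29 to 56 from the survival medians in the background section and call them unreported. Sections 8.4.4 and 8.4.6 still call for later reporting, so no such count is given here.

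**What to change.** Replace the 4-week clause in 8.4.2 with one SAE reporting period, and use it in 8.4.2, 8.4.4, 8.4.5 and 8.4.6. It should cover at least day 0 to day 56 for every infused patient regardless of relapse, progression or transplant, and then continue to the end point already used in 8.4.4 and 8.4.5, once those two are aligned. Copying either of them unchanged is not enough, because both can stop before day 56 and so miss a death that 8.4.3.3 makes an SAE. Because visits may move by 3 days, the day-56 assessment can fall as late as day 59 (56 + 3); the text should say whether the period runs through that visit.

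Section 6.1.3.1 already sets a 56-day minimum follow-up, so the floor fits the existing schedule. Its off-study list, which includes progression, and its removal of transplanted patients should be worded so that they do not cut that minimum short.

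Reconcile 8.4.3.3 with 8.4.3.3.2 on whether aplasia is an SAE when diagnosed on day 42 or only if it persists to day 56.

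The cost is a few sentences of protocol text and slightly more SAE paperwork. No dose, DLT definition or escalation rule changes.
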